- In Part A, for cohorts A1-A4 (with 4 subjects planned), 4 subjects have completed two weeks post-dose in the study. In Part A, for Cohorts A5-A8 and B1-B5 (with 8 subjects planned), 6 subjects must complete two weeks post-dose in the study.
- The majority of subjects dosed with PF-06835375 in a given cohort have a detectable B cell count (obtained from the CLIA certified central lab; LLOQ = 1 B cell per μ L of blood) for a minimum of 2 consecutive visits at least 2 weeks apart, starting at Week 12. Subjects, who reach detectable B cell counts and withdraw from the study earlier, will be considered as having met this criterion. Subjects who withdraw from the study prior to reaching a detectable B cell count will not be counted in the cohort size (this will be limited to 1 subject per cohort of 4 or 2 subjects per cohort of 8). Investigators will have access only to de-identified B-cell count data to remain blinded.
- The sponsor and majority of investigators with active subjects and/or subjects enrolled in the dose level under review (includes only subjects who received IP) agree to proceed to the next dose level based on the overall safety profile. For the purpose of defining the majority of investigators, only one investigator from each site will be counted.

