3.5. Criteria for End of Study

All subjects will be followed through the Week 16 visit. In order for the Week 16 visit to be the subject's last clinic study visit, B cell counts meet at least one of these criteria:

- B cell count is \geq 50% of baseline value AND is stable or increasing between Week 12 and Week 16 measurements, OR
- B cell count is \geq lower limits of normal (defined as 80 cells/ μ l¹⁹) at Week 16.

If at least one of the above criteria are not met at Week 16, subjects will continue in the study and will be followed until B cell count meets at least one of these criteria:

- B cell count is \geq 50% of baseline value AND is stable or increasing between the two measurements at least two weeks apart, OR
- B cell count is \geq lower limits of normal (defined as 80 cells/ μ l¹⁹), OR
- B cell count reaches a new stable (or increasing) detectable level AND subject is clinically stable for minimum of two consecutive visits, each at least two weeks apart, based on the assessment by both the sponsor AND the investigator. The earliest B cell count that can be considered for this criterion is from the Week 20 visit. As a result, subjects will not be discharged prior to availability of Week 24 lab results for B cells under this criterion.

B-cell counts obtained from CLIA certified central lab will be used for this determination.

Baseline value is defined as the average of Screening and Day 1 pre-dose values. In cases where only one value (ie, screening or Day 1 pre-dose) is available, this one value will be used as the baseline. Stable is defined as ± 5 cell/ μ l. Values obtained by the central lab will be used.

B cell counts data will be available only after subject completes the clinic visit due to the required shipment of samples to central lab and their processing time. Once subject meets the criteria for the end of study described above, a phone visit will take place within approximately 1-2 weeks, prior to the next scheduled in clinic visit. This phone visit will be considered the end of study visit/last visit.

Subjects may be asked to return for additional follow up visits beyond the anticipated end of study visit for safety reasons as determined by the Investigator in consultation with the sponsor medical monitor.

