- f. Current or past history of either 1) active tuberculosis (TB) infection or 2) latent TB that was inadequately treated or where adequate treatment cannot be documented.
- g. Clinically significantly abnormal chest X-ray per investigator opinion or evidence of active TB on chest X-ray. Subjects who had chest X-ray performed within 3 months prior to the Screening visit do not have to have chest X-ray performed, provided documentation is available.

13. Known hypersensitivity, intolerance or allergic reaction to the IP or placebo or any of its excipients, or history of severe hypersensitivity to monoclonal antibodies.
14. Known hypersensitivity or allergic reaction to pre- or post-infusion medications (corticosteroids, acetaminophen and antihistamines).
15. Known hypersensitivity or allergic reaction to Td or Trumenba vaccination.
16. Received any live virus or live-attenuated vaccines within 4 weeks prior to Screening, or expected during the study period (from Screening to subject's last visit).
17. Received plasmapheresis within 12 weeks prior to Screening or expected during the study period (from Screening to subject's last visit).
18. History of or planned organ transplant for the duration of the study (from Screening to subject's last visit).
19. Major surgery requiring use of general anesthesia within 6 weeks prior to Screening or planned or expected major surgery during the study period (from Screening to subject's last visit).
20. History of any malignancy within past 5 years prior to Screening (except adequately treated and removed basal and squamous cell carcinomas of the skin, and in situ cervical cancer intraepithelial neoplasia of the uterine cervix).
21. Subject abused drugs or consumed an excessive amount of alcohol in the past 12 months, based on the opinion of the investigator.
22. Presence of any of the following laboratory abnormalities at Screening:
 - B-cell count at Screening below the lower limit of normal (LLN), defined as 80 cells/ μ l (obtained from CLIA certified central lab).

- Total serum IgG <5 mg/dl (or 5 g/l).
- Hemoglobin <10 g/dL (100 g/L).
- White blood cell count <2.5 x 10⁹ /L (<2,500/mm³).
- Platelet count <75 x 10⁹/L per central laboratory results (75,000/mm³).
- Neutrophil count <1.5 x 10⁹/L (<1,500/mm³).
- Aspartate aminotransferase (AST) **or** alanine aminotransferase (ALT) level $\geq 2.0 \times$ upper limit of normal (ULN).

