8.2.3. Pharmacodynamic Analysis

All of the PD endpoints described in the [Section 6.4](#) will be summarized by dose at each time point presented in tabular form or graphically. The descriptive statistics will include standard summaries of absolute concentrations, changes from baseline and percentage change from baseline. The presentations of PD endpoints will include:

- Listing of B and TfH cells sorted by subject ID, treatment group, dose and visit.
- Summary of B and cTfh Cell Depletion Parameters (Mean maximum % decrease from baseline, Mean duration of depletion below 10 cells/ μ L after first dose) following Single Dose Intravenous Administration.

C
C
I
C
C
I
C
C
I
C
C
I

The length of time used for the x-axes of these plots will be decided on review of the data, and will depend on follow-up duration of participants.

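### SAP 8.2.3 reports the duration of depletion below 10 cells/µL as a plain mean, although subjects can leave the study before that duration has ended

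*SAP*

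**What the plan says.** SAP 8.2.3 lists a "Summary of B and cTfh Cell Depletion Parameters (Mean maximum % decrease from baseline, Mean duration of depletion below 10" cells/µL, counted from the first dose, for single intravenous dosing (Part A). The section refers back to SAP 6.4, which names CXCR5 positive B cells and cTfh cells. It also plans summaries by dose and time point and a listing by subject and visit.

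Protocol 3.5 decides when a subject may leave. At Week 16 the B cell count must be at least half of baseline and stable or rising, or at least 80 cells/µL. After Week 16 a third route opens: "B cell count reaches a new stable (or increasing) detectable level AND subject is clinically stable for minimum of two consecutive visits", "based on the assessment by both the sponsor AND the investigator". On timing, "subjects will not be discharged prior to availability of Week 24 lab results for B cells under this criterion". Stable means within 5 cells/µL, and all counts come from the central laboratory. Protocol 3.4.1 gives the lower limit of quantification as 1 B cell/µL. No route mentions cTfh.

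Protocol 6.3 allows withdrawal at any time. Protocol 3.4.1 foresees it during depletion: "Subjects who withdraw from the study prior to reaching a detectable B cell count will not be counted in the cohort size".

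The visible text of SAP Section 7 covers safety imputation, values below quantification, missing concentrations and PK parameters that cannot be calculated. It has no rule for a duration still running at the last visit.

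**The concern.** A mean duration needs an observed end for every subject who contributes. A subject last seen below 10 cells/µL shows only that depletion lasted at least until that visit. The stated statistic has no place for that information. One programmer could stop the clock at the last visit and another could leave the subject out, and they would report different means from the same data.

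How long depletion lasts is one of the PD questions the study sets itself (Protocol 1.2.1, SAP 2). The distortion would be greatest where depletion lasts longest, which is where a reader would look when choosing later doses. Cohorts A5 and A6 have six planned active subjects each, so one subject can move the mean noticeably.

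**Working it through.** The documents give no duration, variance or share of unfinished durations, so there is no plan figure to reproduce. The check has two parts.

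**1. Which routes allow exit below 10?**

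- *B cells, routes 1 and 2 (central-laboratory count).* The exclusion criteria bar a "B-cell count at Screening below the lower limit of normal (LLN), defined as 80 cells" per µL. "Baseline value is defined as the average of Screening and Day 1 pre-dose values", so baseline is at least (80 + 0)/2 = 40 and half of it at least 20. Route 2 needs 80. Neither can release a subject whose central-laboratory count is below 10. This does not carry over to the CXCR5 positive count.
- *B cells, route 3.* Any detectable level will do. Counts of 3 and then 5 cells/µL at Weeks 20 and 24 are detectable and rising, so the subject may leave below 10 if judged clinically stable.
- *cTfh.* Every route uses B cells alone, so a subject may leave from Week 16 whatever the cTfh count.
- *Withdrawal.* This can end either duration at any visit.

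**2. How large could the effect be?**

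Let f be the share of a cohort's active subjects affected, M the mean duration in the others, and u the weeks of depletion after the last visit. M and u are assumptions. A subject below 10 from soon after dosing until a third-route discharge has a duration of at least about 24 weeks.

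*Left out.* The true mean is at least (1 − f)M + 24f and the reported mean is M, so the shortfall is at least f(24 − M). With f = 1/6 (one subject in A5 or A6):

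- M = 8: 16/6 = 2.7 weeks, 25% of the bound of 10.7
- M = 12: 12/6 = 2.0 weeks, 14% of 14.0
- M = 16: 8/6 = 1.3 weeks, 8% of 17.3

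For cTfh, exit can come at Week 16. The same formula with 16 in place of 24 gives 8/6 = 1.3, 4/6 = 0.7 and 0 weeks.

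*Cut at the last visit.* The shortfall is f × u. With f = 1/6 and u = 4, 8 or 16, it is 0.7, 1.3 or 2.7 weeks.

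*No such subject.* The shortfall is 0.

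**Direction.** The bound shows a shortfall from omission only when M is below 24. An illustrative simulation of the visit schedule and exit rules used an assumed return to 1 cell/µL at a median of Week 12, 20 or 28 (CV 30%) and doubling every 2, 4 or 6 weeks. Cutting at the last visit changed the mean by 0% to −32%. Omission changed it by −27% to +83%. The large upward results came only where at least 97% of subjects left below 10. These figures show sensitivity to the handling rule and are not forecasts.

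**The case against.** **Redaction.** The text after this bullet is blacked out, as are parts of SAP 6.4 to 6.6, and SAP Section 1 refers to a separate bSAP. A reader might infer that the plan has no censoring rule. The documents do not support that: a derivation rule could sit in hidden text, the sponsor's standards or the bSAP. What stands is that the visible statistic is a mean, which does not suit durations without an observed end.

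**Assay.** A reader might also infer that the SAP leaves the B cell assay open. SAP 8.2.3 points to 6.4, so the natural reading is the CXCR5 positive count. Naming it in the derivation is a courtesy, not a correction.

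**Low-dose cohorts.** The same formula with 1 of 3 gives larger shortfalls, and a reader might apply them to A1 to A4. At 0.03 mg, Protocol 1.3 predicts about 50% B cell depletion. From a count of 80 that leaves about 40, well above 10. The escalation cap ("this will be limited to 1 subject per cohort of 4 or 2 subjects per cohort of 8") is a counting rule and says nothing about how many such exits to expect.

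**Little depends on it.** No hypothesis is tested, and route 3 needs agreement that the subject is clinically stable. The planned listing would show who was last below 10. All of this is right and limits the weight of the point. The listing does not correct the tabulated mean, however.

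**cTfh.** The documents give no baseline cTfh count. If baseline is already near or below 10, a duration below 10 is poorly defined and censoring alone would not repair it.

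**Conclusion.** The point holds as a minor correction to one descriptive PD summary in Part A. The discharge rules and withdrawal allow B cell and cTfh durations to be right-censored. A mean that stops such subjects at the last visit is too short, and omission distorts it too.

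The size cannot be found from the documents. The 1.3 to 2.7 week minimum rests on one of six subjects being below 10 from soon after dosing to a third-route exit at Week 24 or later, on that subject being left out, and on an assumed mean of 8 to 16 weeks in the others.

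A5 and A6 (3 and 6 mg, per SAP 2.1) are the cohorts of interest. Even there, prolonged depletion is not certain: Protocol 1.3 predicts counts of 1 cell/µL or less for about 8 weeks with two IV doses of 10 to 30 mg, above anything given in Part A. It would go too far to infer that the reported means will be biased, or that omission always shortens them.

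**What to change.** Add a derivation to SAP 8.2.3, applied separately to CXCR5 positive B cells and cTfh:

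- Start is the first post-dose count below 10 cells/µL. End is the first later count of 10 or more. Give the number of subjects who never fall below 10.
- A subject still below 10 at the last available count is right-censored there and listed as '>x weeks'. Give the number censored by dose.
- Report the Kaplan-Meier median (or 'not reached') and the range for every dose, so that statistics are not mixed across doses. Keep the mean as an added figure only where no subject is censored.

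If hidden text already holds such a rule, the sponsor need only confirm it and align the statistic.

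The cost is a few SAP sentences and some extra entries in a planned table. No new data, visits or protocol amendment are needed, and Protocol 3.5 can stay as it is.

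There are three downsides:

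- The median may not be reached in cohorts of 3 to 6. If the censored subjects come last, it is reached with 1 of 3 censored (survival falls to 0.33) or up to 3 of 6 (0.50), but not with 2 of 3 or 4 of 6 (0.67).
- Discharge depends on the B cell count, so B cell censoring is informative. The number censored must be read beside the median.
- Crossing times are known only to within the gap between visits: 2 to 4 weeks from Day 29 to Week 16, 4 weeks to Week 52 and 12 weeks after that. The cTfh sampling schedule is not visible.

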8.3. Safety Analysis

A set of summary tables split by treatment will be produced to evaluate any potential risk associated with the safety and toleration of administering PF-06835375.

No formal analyses are planned for safety data. The safety and other endpoints detailed in [Section 6.2](#) will be listed and summarized in accordance with sponsor reporting standards, where the resulting data presentations will consist of participants from the safety analysis set.

8.3.1. Treatment and Disposition of Participants

Subject evaluation groups will show end of study subject disposition and will show which subjects were analyzed for pharmacokinetics, as well as for safety (adverse events and laboratory data). Frequency counts will be supplied for subject discontinuation(s) by treatment.

Data will be reported in accordance with the sponsor reporting standards.

8.3.2. Demographic and Clinical Examination Data

A breakdown of demographic data will be provided for age, race, gender (at birth), weight, body mass index, height, and primary diagnosis (SLE or RA). Each will be summarized by treatment group in accordance with the sponsor reporting standards. Background medication data will be summarized for each of the treatment groups.

8.3.3. Discontinuation(s)

Subject discontinuations, temporary discontinuations or dose reductions due to adverse events will be detailed and summarized by treatment.

Data will be reported in accordance with the sponsor reporting standards.

8.3.4. Adverse Events

Adverse events will be reported in accordance with the sponsor reporting standards. Several minor ad-hoc adjustments and additions will be conducted.

In the case report forms (CRF) the infusion-related adverse effect was characterized by toxicity grade, instead of the conventional characterization of the AE by severity. The possible toxicity grades are 0,1,2,3,4. The values of toxicity grades = 0, 1, 2 will be mapped to the “mild” category of the AE severity score and values of the toxicity score equal to 3 and 4 will be mapped to the “moderate” and “severe” scores accordingly. The explanation of this mapping from toxicity to severity scale needs to be included into the footnote of the otherwise standard summaries of the adverse events.

Listings with the descriptions of infusion-related reactions (IRR) and injection site reactions (ISR) will be created (separately for all causalities and treatment related adverse events) with the description of individual adverse effects.

Similar listings describing subsets of all events of participants who had preferred term of a special interest that may suggest the occurrence of cytokine release syndrome, with start on Day 1-3 after dose 1 (IV or SC) or Day 1- 4 after dose 2 (SC) will be created (separately for all causalities and treatment related adverse events). The set of preferred term of interest will include tachycardia, hypotension, hypertension, chills, vomiting, nausea, headache, pyrexia, dizziness, and palpitations. The observation of a group of two or more events from this set within a short time window after the dosing will be viewed as a potential cytokine release syndrome event (PCRE). The tabulation showing total number of participants and number and percent of PCREs within each of the doses will be created. Note that this analysis is exploratory and the list of preferred terms may be modified if needed.

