3.4.2. Dose Escalation Stopping Rules

Dose escalation stopping rules will be used to determine whether the maximal tolerated dose has been attained. Dose escalation will be stopped if it is determined that the limits of safety and/or tolerability have been reached based on the criteria described in this section. This decision will be made after a discussion takes place between the sponsor study team and the investigator. The sponsor study team may not overrule the investigator's decision to stop dose escalation. If dose escalation is stopped because of any of these criteria, additional cohorts may receive the same or lower doses of the investigational product.

The dose escalation will be terminated based on the following criteria:

- If ≥ 2 subjects within a dose cohort develop *Common Terminology Criteria for Adverse Events* (CTCAE) v4.0 Grade 3 adverse event considered to be serious (ie, SAE) in the same organ system, or if 1 subject develops a CTCAE v4.0 Grade 4 or higher SAE, considered related to study drug, and not clearly related to the underlying disease (ie SLE or RA) process, concomitant medications or supplements.
- Laboratory abnormalities known to be associated with B-cell depleting therapies (neutropenia, thrombocytopenia and anemia) will not be considered for this criterion, instead these laboratory abnormalities will be considered for Individual Stopping Rules ([Section 3.4.3](#)).
- If 50% or more subjects within a dose cohort experience a CTCAE v4.0 Grade 3 or higher infusion reaction as defined by the criteria in [Appendix 7](#).
- If a confirmed or probable case of Progressive Multifocal Leukoencephalopathy is observed, the sponsor will hold dosing for all subjects until the benefit risk assessment of PF-06835375 is re-evaluated by the sponsor (See [Section 7.1.14](#)). If the sponsor concludes the benefit risk assessment is favorable, investigators will be consulted on whether to proceed as described in this section.
- If, at any dose level, the mean exposure for the treatment group reaches or exceeds the exposure stopping limit of C_{av} of 261 $\mu\text{g}/\text{mL}$, OR, based on the observed data, the group mean C_{av} of the next planned dose is projected to exceed the exposure stopping limit (See [Section 1.3](#)). Modified doses may be explored if they are not expected to exceed PK stopping criteria.

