3.4.3. Individual Stopping Rules

If an individual subject develops any of the following, the subject will not receive a second dose of IP in Part B. Subjects in Part B (MAD cohort) who meet these criteria and who have received the first dose of IP will remain in the study and continue to be followed per the [Schedule of Activities](#):

- Laboratory values meeting criteria for potential drug induced liver injury (see [Section 8.4.2](#)).
- Illness or clinical adverse event that prevents daily activity and requires medical intervention (ie CTCAE v4.0 Grade 3).
- Any serious adverse event (irrespective of relatedness to study drug).
- Any infection requiring the use of oral or parenteral antibiotics between first and second dosing of IP requires approval by sponsor clinician or medical monitor prior to subject receiving a second dose of IP.
- Increase in SLE or RA disease activity requiring use of prohibited medications (See [Appendix 2](#)), OR doses or formulations of medications inconsistent with those allowed (See [Appendix 3](#)).
- Prior CTCAE v4.0 Grade 4 infusion reaction during first infusion.

The following criteria will not be considered as Individual Stopping Rules (due to the anticipated effects of PF-06835375 on blood counts):

- Lymphopenia: CTCAE v4.0 Grade 2 lasting 14 days or less OR Grade 3 lymphopenia lasting 7 days or less. For subjects with abnormalities present on Day 1 prior to dose (ie, CTCAE v4.0 Grade 1 or 2), a two-grade shift lasting 14 days or less.
- Neutropenia: CTCAE v4.0 Grade 2 lasting 7 days or less OR Grade 3 lasting 3 days or less.
- Thrombocytopenia: CTCAE v4.0 Grade 2 lasting 7 days or less OR Grade 3 lasting 3 days or less.

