7.1.12. Infusion Site Reactions

Subjects will be continuously monitored for infusion site reactions from the start of drug administration until the end of infusion and then at time points indicated in the [Schedule of Activities](#). Infusion site reactions may be monitored beyond the time points indicated in the [Schedule of Activities](#) based on investigator's assessment.

Infusion reactions may include but are not limited to: rash, flushing, hypotension, tachycardia, throat irritation or discomfort, difficulty swallowing, fever, chills. Any signs or symptoms related to either an infusion or injection site reaction(s) should be treated according to the investigator's standard of care and reported as adverse events. See [Appendix 7](#) for details regarding the grading of adverse events arising from infusion reactions. Infusion reactions will be categorized according to the following definitions:

1. **Acute:** From start of infusion to 2 hours after the infusion. Infusion reaction AEs that occur during this time period be further classified as follows:
 - a. **Serious:** Infusion reactions that meet the criteria of an SAE.
 - b. **Dose interrupted:** Associated with temporary or permanent interruption and/or modification in dose.
 - c. Infusion reaction AEs based on investigator's judgment.
2. **Immediate:** 2 hours after the infusion to 24 hours after initiation of treatment. Infusion reaction AEs that occur during this time period can be further classified as follows:
 - a. **Serious:** Infusion reactions that meet the criteria of an SAE.
 - b. Infusion reaction AEs based on investigator's judgment.
3. **Late (delayed):** 2 days to 14 days after initiation of treatment:
 - a. **Serious:** Infusion reactions that meet the criteria of an SAE.
 - b. Infusion reaction AEs based on investigator's judgment.

Information regarding infusion reactions will be collected on the Adverse Event Record. If the infusion reaction requires a modification to the administration of test article, the information must be recorded on the Test Article Record. All infusion reactions that are considered SAEs should be reported as specified in [Section 8.2.3](#).

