8.3. Severity Assessment

If required on the AE page of the CRF, the investigator will use the adjectives MILD, MODERATE, or SEVERE to describe the maximum intensity of the AE. For purposes of consistency, these intensity grades are defined as follows:

MILD	Does not interfere with subject's usual function.
MODERATE	Interferes to some extent with subject's usual function.
SEVERE	Interferes significantly with subject's usual function.

Note the distinction between the severity and the seriousness of an AE. A severe event is not necessarily an SAE. For example, a headache may be severe (interferes significantly with the subject's usual function) but would not be classified as serious unless it met one of the criteria for SAEs, listed above.

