Cytokine release syndrome/acute infusion reaction	Cytokine release	Mild reaction; infusion interruption not indicated; intervention not indicated	Requires therapy or infusion interruption but responds promptly to symptomatic treatment (eg, antihistamines, NSAIDS, narcotics, IV fluids); prophylactic medications indicated for ≤ 24 hrs	Prolonged (ie, not rapidly responsive to symptomatic medication and/or brief interruption of infusion); recurrence of symptoms following initial improvement; hospitalization indicated for other clinical sequelae (eg, renal impairment, pulmonary infiltrates)	Life-threatening; pressor or ventilatory support indicated	Death

Remark: Cytokine release syndromes/acute infusion reactions are different from Allergic/hypersensitive reactions, although some of the manifestations are common to both AEs. An acute infusion reaction may occur with an agent that causes cytokine release (eg, monoclonal antibodies or other biological agents). Signs and symptoms usually develop during or shortly after drug infusion and generally resolve completely within 24 hrs of completion of infusion. Signs/symptoms may include: Allergic reaction/hypersensitivity (including drug fever); Arthralgia (joint pain); Bronchospasm; Cough; Dizziness; Dyspnea (shortness of breath); Fatigue (asthenia, lethargy, malaise); Headache; Hypertension; Hypotension; Myalgia (muscle pain); Nausea; Pruritis/itching; Rash/desquamation; Rigors/chills; Sweating (diaphoresis); Tachycardia; Tumor pain (onset or exacerbation of tumor pain due to treatment); Urticaria (hives, welts, wheals); Vomiting.

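### The SAP recodes Grade 2 infusion reactions as mild and Grade 3 as moderate, one level too low, so the primary safety tables will understate severe reactions

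*SAP*

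**What the plan says.** SAP Section 8.3.4 explains that infusion-related events carry a toxicity grade on the CRF instead of the usual severity category. On the range of that grade it states: "The possible toxicity grades are 0,1,2,3,4". The conversion puts the three lowest grades together as mild. For the two highest grades the SAP's rule is: "values of the toxicity score equal to 3 and 4 will be mapped to the “moderate” and “severe” scores accordingly". The converted values go into the otherwise standard adverse event summaries, with a footnote explaining the mapping. The SAP calls these changes minor and ad hoc and gives no rationale for the cut-points.

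The protocol bears on this in five places:

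- Section 2 makes the severity of treatment-emergent adverse events part of the primary endpoints.
- Section 7.1.12 refers the reader to Appendix 7 "for details regarding the grading of adverse events arising from infusion reactions". Appendix 7 is a CTCAE table running from Grade 1 to Grade 5.
- Section 8.3 defines the three severity levels by interference with usual function. The definition of severe opens "Interferes significantly with subject".
- Section 3.4.3 lists as an individual stopping criterion "Illness or clinical adverse event that prevents daily activity and requires medical intervention (ie CTCAE v4.0 Grade 3").
- Section 3.4.2 ends escalation "If 50% or more subjects within a dose cohort experience a CTCAE v4.0 Grade 3 or higher infusion reaction".

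**The concern.** The conversion lowers the severity of one class of event only, and Protocol Section 1.6 describes that class as dose-dependent and potentially severe. All other adverse events are rated directly on the Section 8.3 scale. Injection site reactions in the SC cohorts are graded under Appendix 8, where pain that stops daily activity is already severe. An infusion reaction with the same effect on the subject would be tabulated as moderate.

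At stake is how a primary endpoint reads. The severe column for the IV cohorts could be empty, or nearly so, when reactions graded 3 had occurred. Anyone comparing IV with SC, comparing infusion reactions with other events, or carrying the counts into a later safety summary would start from figures that the protocol's definitions do not support.

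**Working it through.** The documents give no figure to reproduce here. The check sets the SAP conversion beside the protocol's descriptions and then counts what each mapping would show.

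**1. Grade by grade**

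| Grade | Protocol Appendix 7, paraphrased | SAP severity | Severity consistent with the protocol | Shift |
|---|---|---|---|---|
| 0 | Not defined | Mild | None; query the record | Undefined |
| 1 | Cytokine release: mild, no intervention. Rigors: labelled mild | Mild | Mild | None |
| 2 | Cytokine release: therapy or infusion interruption, prompt response. Rigors: labelled moderate | Mild | Moderate | One level down |
| 3 | Cytokine release: prolonged or recurrent, or "hospitalization indicated for other clinical sequelae". Allergic reaction: symptomatic bronchospasm, angioedema or hypotension. Rigors: labelled severe | Moderate | Severe | One level down |
| 4 | Cytokine release: life-threatening. Rigors: no such grade | Severe | Severe | None |
| 5 | Death | Not mapped | To be stated | Undefined |

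The rigors and chills row is the most direct evidence, because it attaches the words mild, moderate and severe to Grades 1, 2 and 3. It has no Grade 4, so a reaction graded on that row could never be tabulated as severe under the SAP. Section 3.4.3 points the same way: it equates Grade 3 with an event that stops daily activity and needs medical intervention, which goes beyond the Section 8.3 definition of moderate (some interference with usual function).

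**2. A cohort at the escalation-stopping threshold**

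Take a cohort that just reaches the 50% criterion of Section 3.4.2, with all reactions at Grade 3:

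- 8 subjects: 8 × 0.5 = 4 with Grade 3. Severe under the SAP: 0 of 8. Severe under the protocol-consistent mapping: 4 of 8 (50%).
- 4 subjects: 4 × 0.5 = 2 with Grade 3. Severe under the SAP: 0 of 4. Severe under the protocol-consistent mapping: 2 of 4 (50%).

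Counting active subjects only gives the same picture: 0 against 3 of 6, or 0 against 2 of 3.

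**3. Illustration across the IV cohorts used**

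SAP Table 1 shows A1 to A6 as the IV cohorts used. Planned active subjects: 4 × 3 + 2 × 6 = 24. The documents give no Grade 3 or Grade 4 rates, so the rates below are assumptions. Expected severe subjects are 24 × p4 under the SAP and 24 × (p3 + p4) under the protocol-consistent mapping. The chance of at least one Grade 3 subject is 1 − (1 − p3)^24.

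| Assumed p3 | Assumed p4 | Severe, SAP | Severe, protocol-consistent | Chance of at least one Grade 3 |
|---|---|---|---|---|
| 5% | 0% | 0 | 1.2 | 71% |
| 10% | 1% | 0.24 | 2.64 | 92% |
| 20% | 2% | 0.48 | 5.28 | over 99% |

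Over this range the difference between the two mappings is 24 × p3, that is 1.2 to 4.8 subjects out of 24.

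**The case against.** Several points on the other side are fair.

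- The SAP speaks of a toxicity grade and does not name CTCAE. Its range of 0 to 4 differs from the 1 to 5 of Appendix 7, and the CRF is not available. The link is therefore an inference. It stands because Section 7.1.12 directs the grading to Appendix 7 and neither document offers another scale for infusion reactions.
- Only Grades 2 and 3 move. Grade 1 stays mild and Grade 4 stays severe. Counting Grade 0 as mild would, if anything, add events.
- Neither document contains a crosswalk from grade to severity. Some Grade 2 findings, such as a rash or brief treatment for low blood pressure, might be rated mild by functional interference. Grade 2 as moderate rests on the rigors row and on convention. The case on Grade 3 is stronger.
- The Section 3.4.3 wording on Grade 3 concerns illness and adverse events in general; infusion reactions have their own entry there. Appendix 7 carries more of the weight.
- Injection site reactions already had a separate four-category scale, so IV and SC severity was never fully comparable. The conversion widens that gap.
- The stopping rules use the grade directly and serious events are reported whatever their severity category, so neither escalation decisions nor SAE reporting is affected. The safety analysis is descriptive, and the conversion applies equally to active and placebo.
- The footnote discloses the conversion, individual infusion reactions are listed, and possible cytokine release events are tabulated by dose.

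These points limit the consequences but do not rescue the conversion. A footnote and listings tell a reader that grades were recoded; the severe counts in the tables remain wrong.

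**Conclusion.** The concern holds and should be fixed before the tables are produced. As written, the SAP classifies every Grade 2 and every Grade 3 infusion reaction one level lower than the protocol's own descriptions support, in summaries that report a primary endpoint. Only Grade 4 can appear as severe, so a cohort meeting the 50% stopping criterion on Grade 3 reactions alone would show 0% severe.

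The conclusion assumes that the CRF toxicity grade is the Appendix 7 grade. Severe reactions are undercounted only if Grade 3 reactions are recorded, and moderate ones are shown as mild only if Grade 2 reactions are. The documents report no observed grades, so the actual number affected is unknown.

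**What to change.** In SAP Section 8.3.4:

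- Tabulate infusion-related reactions by the CTCAE grade recorded.
- Where the combined adverse event tables need three levels, map Grade 1 to mild, Grade 2 to moderate, and Grade 3 or higher to severe.
- Query any Grade 0 record; do not count it as a mild event.
- Name the grading scale, reconcile the CRF range of 0 to 4 with the 1 to 5 of Appendix 7, and state how Grade 5 would be shown.
- Rewrite the footnote to match.

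The cost is SAP wording, one derivation and a rerun of the affected tables. Apart from any Grade 0 queries, no new data are needed. The severe count can only stay the same or rise, so the tables may look less favourable.
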